Our *long-term goal* is to improve global sustainability and enhance food security while improving the competitiveness of the U.S. food system by reducing U.S. household food waste. To reduce household food waste, we must first improve the accuracy, convenience and standardization of its measurement so that evaluations of waste reduction initiatives have more statistical power, less statistical bias, less measurement error, and greater representativeness of targeted populations. Such improved evaluative capacity can stimulate research and program assessment, which then guides prioritization of emerging private and public programs and policies aimed at reducing household food waste.

Specific objectives include:

- (1) Development of FoodImage, a smartphone app that measures household food waste and food-waste-related behaviors,
- (2) Assess differences in the accuracy, time burden and perceived convenience of measurements taken with the FoodImage app versus the current state-of-the-art household food waste measurement approach (a pen-and-paper diary), and
- (3) Use the FoodImage app in a pilot randomized controlled trial designed to evaluate the effectiveness of reducing household food waste through behavioral nudges in the form of personalized feedback about food waste levels and household-specific reduction goals.

Background

About one-third of U.S. food is wasted with two-thirds of this waste attributed to consumers. The United States proposes to cut food waste in half by 2030 and, while many policies are available, those that change consumer waste behavior will be integral to achieving U.S. goals. However, we lack quality data about household food waste because popular data collection methods (diaries and waste stream analyses) suffer major shortcomings. Hence, rigorous evaluation of consumer interventions prove elusive.

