It is estimated to take up to 1 year to recruit participants for this study. It will take approximately 3 years to complete the study and all data analyses. Participation in this study will take approximately 3-4 weeks. The length of participation is virtually identical for participants who complete Phase I and II vs. Phase II only. This is due to Phase I including about one to two hours of laboratory-based procedures prior to participants being trained and asked to use the FoodImage app to track food waste for 4 to 7 days over the subsequent week. Participants who only complete Phase II will not conduct the laboratory-based procedures but all other procedures will be identical.

Study Endpoints

The primary endpoint of this study is food waste and food waste behavior. We will explore these endpoints via the following aims and objectives:

- Development of FoodImage, a smartphone app that measures household food waste and food-waste-related behaviors; and assess differences in the accuracy, time burden of, and perceived convenience of measurements taken with the FoodImage app versus the current state-of-the-art household food waste measurement approach (a pen-and-paper diary) with and without a food scale
- Use the FoodImage app in a pilot randomized controlled trial designed to evaluate the effectiveness of reducing household food waste through behavioral nudges in the form of personalized feedback about food waste levels and household-specific reduction goals.

All data from the FoodImage app (including home address and GPS coordinates from food images) will be used as a study endpoint.

Procedures and Visit Description

The study will accomplish three activities:

- 1) Development of the FoodImage Smartphone app
- 2) Testing the FoodImage app with consumers in a lab setting (Phase I)
- 3) Randomized Controlled Trial of behavioral nudges to reduce household food waste (Phase II)

FoodImage App Development

The programming and development team that created a previous app called SmartIntake® agreed to build the FoodImage app. Originally, we expected the FoodImage app to rely on some features of the SmartIntake app, though FoodImage was ultimately built from scratch. The FoodImage app sends participants' images and accompanying data (e.g., receipts, food descriptions, Participant ID number, and timestamp) to a secure PBRC server where a team will analyze the images to estimate food waste.

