Phase II of this study is a randomized controlled trial of behavioral nudges via the FoodImage app to reduce household food waste. Phase II will occur in participants' natural environment (free-living conditions) and will include the 24 participants enrolled in Phase I and an additional 20 participants. Phase II, participants will be trained to use the FoodImage app to capture data on food purchases, food waste that occurs during food preparation, food waste that is present after eating, and food waste from food purges in free-living conditions. During data collection, subjects will record the source, reason, and destination of all food waste in the app.

Participants will use the app to collect food waste data for approximately 4 to 7 days over the first week of Phase II and these data serve as baseline data. Participants will then be provided with approximately a one-week break where they will not use the app to track food waste (or do any other study procedures). After the one-week break, participants will return to the center and will be randomly assigned (1:1 ratio) to one of the following groups:

1. Stress Management (Control Group). These participants will use the app to record food waste for approximately 4 to 7 days over the subsequent week. They will also receive information on stress management (Appendix C.1).
2. Food Saver (Intervention Group). These participants also will use the app to record food waste for approximately 4 to 7 days over the subsequent week. They will also be provided with the following:
 - a. Feedback on the amount of food waste their household created during the first week,
 - b. A goal to reduce the next week's food waste by 20% or more, and
 - c. Tips on how to reduce household food waste adapted from current consumer campaigns (e.g., Food: Too Good to Waste Implementation Guide and Toolkit, EPA 2016). This includes advice to limit purchases of unnecessary foods, donate or freeze unwanted and unspoiled foods, prioritize keeping and then eating left-overs, minimize waste during food preparation by preparing and serving smaller portions, purchase only needed foods, and purchase foods that are not near the expiration date (see Appendix C.2). A PBRC staff member will deliver tips to each respondent in this group via in-person and remote sessions (call, text, email, videoconference etc.).

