- *User Satisfaction Survey*- This survey asks questions to help staff understand participants' satisfaction with using an iPhone app (FoodImage) to take and send photos of food waste (Appendix B.2.c).

- *Food Environment Questionnaire*- This questionnaire asks questions about purchasing food for the household (Appendix B.2.d).
- *Waste Toss Methods Questionnaire*- This questionnaire asks questions about how participants typically dispose of food in their household (Appendix B.2.e).
- *Food Waste Tip Questionnaire* – This questionnaire asks questions to help staff understand participants' satisfaction with receiving training tips to help reduce food waste (Appendix B.3.a).

Data Analysis and Specimen Management

Phase I analysis objectives include:

- 1) Determining if food waste measured with the FoodImage app is equivalent to the criterion value (directly weighed food waste) for each source (plate waste, food purges, etc.). Error (the difference between food waste measured with the FoodImage app and the criterion value) will also be quantified for each source.
- 2) Determining if food waste measured with each of the pen-and-paper diary methods (with and without a kitchen scale) is equivalent to the criterion value for each source. Error will also be quantified for each source.
- 3) Determining if the error from the FoodImage app is smaller than error from the pen-and-paper records.
- 4) Determining if satisfaction ratings differ significantly between the app and the pen-and-paper record approaches.
- 5) Determining if the amount of time respondents took to complete measurements differed between the app and diary approaches.
- 6) Qualitative assessments by respondents of the desirable and undesirable features of the app and pen-and-paper records.
- 7) Determining if the variance of waste measures differed between the app and pen-and-paper record approaches.
- 8) Assessing the accuracy of receipt data as captured by participants using the app.

Power Analysis. We base our power analysis on plate waste data gathered from previous research conducted at PBRC [20]. With an N of 24, we are powered to detect equivalence within 20 grams with power of 0.80 and alpha of 0.05. Also, *t*-tests to determine if the error from the app (weighed food waste minus estimated waste) differs significantly from the error from the diary method is powered to detect differences as small as 12.8 grams.

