It is hypothesized that food waste will be equivalent (within 20 grams) when measured with the app vs. direct weights of food waste, while food waste measured with the diary method will not be equivalent to directly weighed food waste. It is also hypothesized that the error from the app will be significantly smaller than error from the diary method.

Phase II analysis objectives include:

- 1) Quantifying baseline distributions for total weight of household food waste

- 2) Determining the effectiveness of the behavioral nudge in altering
 - a) Total daily weight of household food waste,
 - b) Total daily weight of each source of household food waste by occasion, including
 - i) plate waste,
 - ii) food prep waste,
 - iii) purge waste,
 - c) Total daily weight of each source of food waste by food type (e.g., dairy, meat, fruits, etc.) and by macronutrient,
 - d) Daily percent of served food that is wasted, and
 - e) Total amount of food purchased by weight and value.
- 3) Quantifying satisfaction levels with the FoodImage app as measured in Appendix B.1.a. (User Preference Survey) and Appendix B.2.c (User Satisfaction Survey),
- 4) The demographic, household and attitudinal factors measured in Appendix B.2.d (Food Environment Questionnaire) related to
 - a) Effectiveness of the behavioral nudge intervention in reducing food waste generated and all subcomponents listed above, and
 - b) Satisfaction levels with the app as measured in Appendix B.2.c (User Satisfaction Survey).

Withdrawal of Subjects

Subjects may be withdrawn from the study if they are non-compliant with study procedures and they will be notified of their withdrawal via telephone or mail. Subjects may voluntarily withdraw from the study at any time. No additional data will be collected and they will be considered drop outs in the study.

Risks to Subjects

This study involves no greater than minimal risk. The main risk is breach of confidentiality, and the PBRC team will work to minimize this during data collection, handling, and analysis.

Potential Benefits to Subjects

Participants may benefit by increased awareness of their food waste behaviors.

Setting

All research procedures will be conducted at PBRC and in participants' natural environment.

Resources Available

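### Does Phase II need a named main outcome and a stated model for the baseline week before its group comparison can be trusted?

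*Combined protocol and SAP*

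**What the plan says.** Specific objective 3 and Study Endpoints give the purpose of Phase II: "Use the FoodImage app in a pilot randomized controlled trial designed to evaluate the effectiveness of reducing household food waste through behavioral nudges". Study Endpoints also states that "The primary endpoint of this study is food waste and food waste behavior", which covers both phases and fixes no variable, unit or time point.

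Under Data Analysis, Phase II objective 1 is "Quantifying baseline distributions for total weight of household food waste". Objective 2 is "Determining the effectiveness of the behavioral nudge in altering" items (a) to (e). Item (a) is "Total daily weight of household food waste". The others are weight by source, weight by food type and macronutrient, the share of served food that is wasted, and purchases by weight and value. Objective 4a then asks which factors relate to the nudge's effect on food waste and on its subcomponents.

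Phase II (Overview) has participants "collect food waste data for approximately 4 to 7 days over the first week of Phase II and these data serve as baseline data". Randomisation, 1:1, follows at Visit 2. The Food Saver group is told how much its household wasted in that week and is asked to cut the next week's "food waste by 20% or more".

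The only power statement belongs to Phase I: with 24 participants, "we are powered to detect equivalence within 20 grams with power of 0.80 and alpha of 0.05". The t-tests and hypotheses given beside it are also for Phase I. No test or model is named for Phase II.

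**The concern.** A trial meant to evaluate effectiveness would normally name one outcome and one comparison. Here objective 2 holds seven countable outcomes (one under a, three under b, one under d, two under e) and an open number under (c), all unranked. The baseline week is collected, but its only stated analytic use is descriptive.

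Two things could be at stake. First, if an analyst tried several outcomes or several models and reported the most favourable, the error rate would rise. Second, even without selection, different treatments of baseline give different estimates in a small trial whenever the arms differ by chance before the intervention. A pilot's estimate feeds the planning of later work, so a reader might want its definition settled in advance.

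**Working it through.** **Inputs.** Phase II has 44 participants (Number of Subjects), randomised 1:1 (Phase II Overview), so 22 per arm if all complete. The documents give no Phase II SD, week-to-week correlation r, alpha or power. The following are therefore assumptions: complete data, normal outcomes with SD 1 in both weeks, two-sided 0.05 and 80% power as a yardstick only, and r = 0.1, 0.3, 0.5, 0.7.

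**The plan's own figure.** There is none for Phase II. The Phase I figures (20 g and 12.8 g) come without an SD, so they cannot be reproduced, and they do not bear on this comparison.

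**Step 1: how often the arms differ at baseline.** The standard error of the baseline difference is √(2/22) = 0.302 SD. A difference of 0.30 SD or more in either direction then has probability 2 × [1 − Φ(0.30/0.302)] = 0.32. A gap of 0.30 SD is thus about one standard error, an ordinary chance imbalance.

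**Step 2: what such a gap does when there is no true effect.** Conditional on a baseline gap of 0.30 SD, the expected estimates are r × 0.30 for follow-up only, (r − 1) × 0.30 for change score, and 0 for ANCOVA.

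| r | Follow-up only | Change score | ANCOVA |
|---|---|---|---|
| 0.1 | +0.03 | −0.27 | 0 |
| 0.3 | +0.09 | −0.21 | 0 |
| 0.5 | +0.15 | −0.15 | 0 |
| 0.7 | +0.21 | −0.09 | 0 |

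The first two columns always differ by exactly 0.30, because follow-up-only minus change-score equals the baseline gap by definition. That contrast sets the two extreme methods against each other. The distance of either from ANCOVA is smaller: 0.03 to 0.21 SD, or 0.09 to 0.27 SD.

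**Step 3: precision.** Detectable difference by noncentral t, 22 per arm. Follow-up only: 0.865 SD on 42 df. Change score: 0.865 × √(2(1 − r)). ANCOVA: 0.876 × √(1 − r²), where 0.876 is the value on 41 df with variance inflation 1 + 1/40.

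| r | Follow-up only | Change score | ANCOVA |
|---|---|---|---|
| 0.1 | 0.865 | 1.160 | 0.872 |
| 0.3 | 0.865 | 1.023 | 0.836 |
| 0.5 | 0.865 | 0.865 | 0.759 |
| 0.7 | 0.865 | 0.670 | 0.626 |

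ANCOVA equals follow-up only at r = 0.16. At r = 0 it is worse by 0.876/0.865 = 1.013, about 1%. At r = 0.3 its advantage is about 3% (0.836 against 0.865). A material gain needs a correlation that the documents do not supply.

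**Step 4: is the main outcome really open?** Total weight is the sole variable in objective 1 and the first item of objective 2. The amount of waste is also what is fed back to Food Saver households and what the 20% goal refers to. Objective 4a treats food waste as the parent quantity with parts beneath it. The share of served food wasted and the purchase outcomes do not fit neatly as parts, but no other item competes for first place.

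**The case for a change.** The best case for acting is that the wording is about effectiveness, not feasibility, so the pilot label excuses missing power but not an undefined effect. In about one trial in three, two competent analysts using the extreme methods would report estimates at least 0.30 SD apart from the same data. If the analysis were chosen for its result, the harm would be larger: taking the best of the three models raises type I error from 5% to about 9.4 to 9.9% in simulation at r = 0.3 to 0.7. Testing seven independent outcomes at 0.05 gives 1 − 0.95⁷ = 30%, and less if they are positively correlated. A remedy would cost only a few sentences.

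The factual part stands: the outcome label and the model are absent, and the missing appendices, described as training materials, records, questionnaires, interview guides and group materials, would not supply them. The consequence does not carry the same weight. The error-rate figures require selection on results, which nothing in the plan invites, and Phase II sets no hypothesis or alpha for such an error to be measured against. The spread between methods is a property of any small trial with a chance imbalance, and each method remains unbiased over randomisations.

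Reading the 20% goal as a target effect does not help either. It is a behavioural goal given to participants, and any power figure for it rests on an assumed SD. It would speak to sample size, not to the choice of model.

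Nor would naming a model close the matter. The plan lets participants record on about 4 to 7 days, so an analyst must still separate a day with no waste from a day not logged, whichever model is used.

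**Conclusion.** No change to the plan is called for. Phase II leaves its main outcome unlabelled and its use of baseline unstated, but no rule, number or analysis that it does state is wrong. The documents point to total daily household waste weight, and the baseline week is plainly there to be used. A sensible analyst would compare the arms on that outcome with baseline taken into account, give an interval, and treat the remaining outcomes as descriptive or exploratory.

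The choice among the three methods moves the estimate by at most 0.27 SD from ANCOVA at a baseline gap of 0.30 SD, over correlations of 0.1 to 0.7. It costs or gains between about 1% and a correlation-dependent amount in precision. These sizes assume 22 completers per arm, normal outcomes and equal variances; larger gaps would scale the shift in proportion. For a minimal-risk pilot with no Phase II power target, this is missing detail of the kind that analysts fill, and its absence does not undermine the trial.

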Study staff will keep in contact with participants over their free-living data collection to ensure data quality and participant compliance.

All participants will have an approximate one-week break after they finish collecting data for ~4 to 7 days during the week following Visit 1. This results in approximately 2 weeks between Visits 1 and 2.

Visit 2 (V2) – Phase I and Phase II enrollees (~Day 14)

Visit 2 will last approximately 3 hours for both Phase I and Phase II participants. Participants will be contacted by study staff before the date of V2 to remind them of their appointment.

Procedures at V2 include:

- Body weight will be measured and recorded by study staff
- Randomization to either:
 - Stress Management group (these participants will receive information from a study interventionist about stress management via an in-person meeting during Visit 2 and via the multimedia capabilities of a smartphone, e.g., text messages, emails, phone calls)
 - Food Saver group (these participants will receive information from a study interventionist about reducing food waste via an in-person meeting during Visit 2 and via the multimedia capabilities of a smartphone, e.g., text messages, emails, phone calls)
- Receive refresher training on use of the FoodImage app to collect data in their home setting for approximately 4-7 days over the subsequent week. Participants' follow-up visit, or Visit 3 (V3) scheduled.

Visit 3 (V3) – Phase I and Phase II enrollees (~Day 21)

Visit 3 will last approximately 1.5 to 2 hours for both Phase I and Phase II participants. Prior to V3, participants will receive a phone call to remind them of their appointment. Procedures at V3 include:

- Review the data collected over the free-living period and discuss the implementation of the stress management or food waste reduction suggestions.
- Complete the following questionnaires:
 - Food Environment Questionnaire
 - Waste Toss Methods Questionnaire
 - User Satisfaction Survey
 - Post-Study System Usability Questionnaire (PSSUQ)
 - Food Waste Tip Questionnaire (Intervention/Food Saver Group only)
- Complete a focus group or cognitive interview to assess thoughts and attitudes towards the app, pen-and-paper records, food environment, and food waste behaviors (Phase I participants only).
- Body weight will be measured and recorded by study staff

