Additional visits are possible if more assistance is needed with the app or to resolve data collection problems, such as technical challenges with the app. These may be in-person, via email, via text or any other mode of communication.

Table 1. Schedule of Visits and Procedures		Phase 1 Enrollees	Phase 2 Enrollees
N		24	20
Phase 1			
Visit 1 (V1): Day 0		~4 Hours	~2.5 Hours
Consent, eligibility verification, Lifestyle and Demographics Questionnaire, body weight, height, BMI		X	X
Training on and use of the app and pen-and-paper records to capture food waste data in laboratory setting		X	
User Preference Survey, PSSUQ, User Satisfaction Survey		X	
Phase 2 (the following procedures occur at the end of Visit 1)			
Training on use of app to collect data in free-living setting.			
Instructed to collect food waste data with the app for approximately 4 to 7 days over the following week. Instructed to then take approximately a one-week break, with Visit 2 occurring at the end of the break.		X	
Visit 2 (V2): ~Day 14		~3 Hours	
Randomization to the Stress Management or Food Saver group and delivery of each groups' instructions and materials		X	
Refresher training for use of app to collect data in the home setting for approximately 4 to 7 days over the next week. Additional training, information, and behavioral nudges will be deployed via phone, email, and text until Visit 3, which will occur approximately one-week later.		X	
Body Weight		X	
Visit 3 (V3): ~Day 21		~<2 hours	
Meeting with staff to discuss collected data and implementation of behavioral nudges		X	
Food Waste Tip Questionnaire		X (Food Saver group only)	
Focus groups or cognitive interviews		X (Phase I participants only)	
Food Environment Questionnaire, Waste Disposal Methods Questionnaire, PSSUQ, User Satisfaction Survey		X	
Body Weight		X	

Description of Questionnaires

- *Eat, Prep, and Toss food waste records*- These pen and paper records will be used during Phase I and are consistent with previous food waste studies (Appendix A.1.e & A.1.f).
- *User Preference Survey*- This survey asks questions to help staff understand participants' acceptability and preference for using the FoodImage app and pen-and-paper records to record food waste (Appendix B.1.a).
- *Post-Study System Usability Questionnaire (PSSUQ)*- This is a validated questionnaire to assesses satisfaction with electronic platforms [19], such as the FoodImage app (Appendix B.2.b).

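### Objective 4a uses a questionnaire given only after randomization and a week of nudges to explain who benefited from the nudge

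*Combined protocol and SAP*

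**What the plan says.** The Phase II analysis objectives in the combined protocol and SAP include, as objective 4, "The demographic, household and attitudinal factors measured in Appendix B.2.d (Food Environment Questionnaire) related to" two things: how well the nudge works on waste and its components (4a), and satisfaction with the app (4b). No model or test is given for 4a.

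The Food Environment Questionnaire appears in the procedures list for Visit 3 and in no other visit's list. Table 1 agrees: its Visit 3 block has the row "Food Environment Questionnaire, Waste Disposal Methods Questionnaire, PSSUQ, User Satisfaction Survey". Visit 3 is at about Day 21.

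Allocation comes earlier. The Visit 2 block of Table 1 (about Day 14) begins "Randomization to the Stress Management or Food Saver group and delivery of each" group's materials, and then states that "Additional training, information, and behavioral nudges will be deployed via phone, email, and text until Visit 3".

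The Description of Questionnaires says of this instrument: "This questionnaire asks questions about purchasing food for the household". The Food Saver tips in the Phase II overview include "advice to limit purchases of unnecessary foods".

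**The concern.** A factor used to explain who responded to an intervention should be one that the intervention could not have changed. Here every answer available to 4a is collected after allocation, and the questionnaire's subject overlaps with what the Food Saver arm is advised to change. The plan itself treats purchasing as something the nudge may alter, since the amount of food bought is an outcome under objective 2e.

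A finding that people with a certain attitude or shopping habit responded better could not then be told apart from people who responded better coming to report that attitude or habit. With no pre-randomization copy of the questionnaire, analysis cannot separate the two. What is at stake is the interpretation of one moderator objective, not the randomized comparison.

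**Working it through.** **Timing.** Day 21 minus Day 14 is about 7 days between randomization and the questionnaire, all of it under intervention. At Visit 3 both arms also have this step: "Review the data collected over the free-living period and discuss the implementation of the stress management or food waste reduction suggestions". It is listed ahead of the questionnaires, although the documents do not say that the order is fixed. No section limits 4a to baseline or time-fixed items.

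**What exists before randomization.** All participants complete the Lifestyle and Demographics Questionnaire at Visit 1. For Phase II, "participants will be trained to use the FoodImage app to capture data on food purchases", and the first week of app data is the baseline. Objective 4 cites neither source. What is missing is an early copy of the Food Environment Questionnaire, chiefly its attitude items.

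**Size.** The plan has no figure on this point to reproduce; its only power statements are for Phase I. The following is an illustration, and everything except the sample size and the 1:1 allocation is assumed.

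- n = 44, 22 per arm; T = 1 for Food Saver, 0 for control.
- Waste reduction R = (0.5 + u)T + e, with e of SD 1 and u (individual variation in response) of SD 0, 0.5 or 1.0.
- True baseline factor M0 of SD 1, unrelated to u and e, so there is no true interaction.
- The Visit 3 answer is M0 plus a shift or a link L times the tracked quantity.
- Fit R = b0 + b1·T + b2·M + b3·T·M and test b3 at 5% on 44 − 4 = 40 df, with 20,000 replicates per cell.

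Measured before randomization, the rejection rate is 0.050 (u SD 0.5) and 0.049 (u SD 1.0). A uniform shift of Food Saver answers by 0.2 to 1.0 gives the same rates. This is exact: replacing M by M0 + cT only moves a constant into b1 and leaves b3 unchanged.

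| Visit 3 answers follow | u SD | L=0.1 | 0.2 | 0.3 | 0.5 | 1.0 |
|---|---|---|---|---|---|---|
| Outcome, both arms | 0.5 | 0.051 | 0.054 | 0.056 | 0.061 | 0.062 |
| Outcome, both arms | 1.0 | 0.061 | 0.078 | 0.103 | 0.152 | 0.176 |
| Own response, Food Saver only | 0.5 | 0.050 | 0.052 | 0.056 | 0.066 | 0.096 |
| Own response, Food Saver only | 1.0 | 0.058 | 0.079 | 0.111 | 0.199 | 0.359 |
| Outcome, Food Saver only | 0.5 | 0.065 | 0.112 | 0.184 | 0.358 | 0.619 |
| Outcome, Food Saver only | 1.0 | 0.082 | 0.166 | 0.294 | 0.547 | 0.764 |

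With outcome tracking in both arms and no variation in response, the rate is 0.050-0.051.

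**Why the pattern arises.** If answers follow outcome with link L in an arm where R has variance V, the slope of R on the answer is L·V / (1 + L²·V). Take L = 0.5:

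- Control arm, V = 1: 0.5/1.25 = 0.40.
- Food Saver arm, u SD 0.5, V = 1 + 0.25 = 1.25: 0.625/1.3125 = 0.476, a spurious difference of 0.076.
- Food Saver arm, u SD 1.0, V = 2: 1.0/1.5 = 0.667, a spurious difference of 0.267.
- If controls do not track at all, their slope is 0 and the whole Food Saver slope appears as interaction.

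A separate run of 10,000 replicates with Food Saver-only outcome tracking and u SD 0 gave mean b3 of 0.194, 0.405 and 0.501 at L = 0.2, 0.5 and 1.0. The formula with V = 1 gives 0.192, 0.400 and 0.500.

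**Power.** With a pre-randomization factor and a true interaction of 0.5 SD per SD, simulated power is 0.341.

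**The case against.** The strongest reply is that the deciding fact is not visible. Appendix B.2.d is not in the supplied text. If its items ask about usual or structural circumstances, a week of nudges may barely move them. That stands, and it makes this a possible bias rather than a demonstrated one.

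The interaction model is also an assumption, because the plan states none, and the high rates need strong conditions. With tracking in both arms, 18% requires response variation of SD 1.0, twice the assumed mean effect, together with a link of 1.0. The 36% and 76% figures require in addition that only Food Saver answers track. Seeing one's own results at Visit 3 happens in both arms, so that route alone falls mainly in the low-rate case. These points stand too. The top figures should not drive any decision, and the argument rests on timing.

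Finally, Visit 3 placement has a merit: asking about purchasing before the outcome week could prime controls and dilute objective 2. That is a real trade-off, but it does not remove the problem. Participants have by then already spent a baseline week recording purchases and reasons for waste, so the extra priming should be small, and a text-only remedy avoids it altogether. That the trial is a pilot limits the weight of the point, but the plan does not label 4a exploratory.

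**Conclusion.** The concern holds, as a minor one. The plan relates nudge effectiveness to answers collected only after allocation and about a week of intervention, and nothing in it restricts those answers to items the nudge could not have changed.

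The size is unknown. Under the assumed model, the interaction test's error rate could be anywhere from its nominal 5% upward: no inflation for a uniform shift, and 5-6% to 6-18% for tracking in both arms. Higher values need tracking in the Food Saver arm alone. The conclusion is confined to purchasing and attitude items. Fixed demographic and household items, objective 2 and objective 4b are unaffected. With about 34% power for a 0.5 SD interaction even when the factor is measured properly, 4a is exploratory either way.

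**What to change.** Give the Food Environment Questionnaire before randomization, either at Visit 2 ahead of allocation or at Visit 1, and use only those answers in 4a. Use them together with the Visit 1 Lifestyle and Demographics Questionnaire and the purchase data from the baseline app week. Treat any Visit 3 copy as an outcome. State that 4a is exploratory and report estimates with confidence intervals.

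The cost is one line in the visit schedule and one edited objective, with no added participant time if the questionnaire is moved rather than repeated. The downside is possible priming of both arms: before the baseline week if given at Visit 1, or just before the outcome week if given at Visit 2, where priming of controls could dilute the contrast.

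If that is unwelcome, or the questionnaire cannot be moved, leave it at Visit 3 and limit 4a to time-fixed items and pre-randomization data. This needs only a change of text and adds no priming.
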